Attention	Simple	WAIS-IV Digit Span Forward
	Complex/working mem	WAIS-IV Digit Span Backward
	Complex/working mem	Trails B
Learning/Memory	Immediate	HVLT (versions 1 and 4)

	Delayed	HVLT (versions 1 and 4)
	Psychomotor Speed	Trails A
	Psychomotor Speed	WAIS-IV Digit Symbol Coding
Mood	Anxiety	GAD-7
	Depression	GDS-15

f. Statistical analysis plan

The study population will be described by demographics (e.g. sex, age, race, education status) and baseline health (e.g. vision or hearing impairment, medical history). The appropriate summary measures (mean and standard deviation for continuous variables and frequencies for categorical variables) will be reported. Missing data will be assessed and if a large proportion of data is missing (>10%), we will compare baseline characteristics between subjects to determine if this subpopulation is significantly different. Imputation methods will be considered if differences are found. All statistical analyses will be performed in SAS v9.4 and evaluated at the 0.05 significance level, unless otherwise indicated.

Primary Aim: estimate the incidence of post-operative cognitive dysfunction three months after orthopedic surgical intervention.

This will be defined as a 1.5 SD decline from in any one of the cognitive domains tested baseline to three months. The proportion of patients who develop POCD and a 95% confidence interval will be reported.

Secondary Aim 1: determine pre and peri-operative risk factors associated with development of POCD.

We will be primarily interested in the association between incidences of POCD with the following risk factors:

1. History of delirium
2. Presence of post-operative delirium
3. Regional versus general anesthesia
4. >3 sedating medications added during hospitalization
5. History of prior surgery with general anesthesia

We will fit a logistic regression model with presence of POCD as the outcome of interest and the above risk factors as predictors of interest. We will also include age and gender. As an exploratory analysis, we will fit a model with additional risk factors and use score selection to keep variables with the most impact.

Secondary Aim 2: explore the role of serum neurofilament light (NfL) in predicting risk for development of POCD.

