A logistic regression model will be fit with presence of POCD as the outcome of interest and NfL as the predictor of interest to assess the predictive ability of NfL in the development of POCD. We will fit another logistic model that includes NfL and adjusts for the risk factors called out in Secondary Aim 1.

g. Power analysis or statement of precision

In 2018, the orthopaedic center conducted 355 primary knee, 283 primary hip, and 76 primary shoulder/reverse shoulder surgeries. Approximately 450 of these were completed by Drs. [name] and [name], from whose patient populations we will be recruiting. This excludes non-elective cases, revisions, removals, supplements, and unis. The goal of the study is to recruit n=100 subjects. This n was based on both the number of patients we expect to be able to recruit during our timeline, and the estimated study budget. We anticipate the POCD incidence rate will be between 18 and 25% based on previous literature (Moller T et al Lancet 1998). A sample size of 100 produces a two-sided 95% confidence interval with a width equal to 0.157 when the sample proportion is 0.2. This calculation was done using the confidence intervals for one proportion procedure of PASS 2016.

h. Strengths and limitations

Strengths of this study include its focus on post-operative cognitive dysfunction, a topic that is not widely covered in the neurology, orthopedic or anesthesia literature. Furthermore, this study represents a more robust improvement over past investigations of post-operative cognitive dysfunction in normal aging adults in that the Montreal Cognitive Assessment (MOCA) rather than the Mini Mental Status Exam (MMSE) is being used to confirm normal cognition. The MOCA has a 90% sensitivity for mild cognitive impairment whereas the MMSE has an 18% sensitivity for mild cognitive impairment. This will be one of the first studies to evaluate patients exclusively undergoing elective orthopedic surgery whereas prior studies have looked at POCD following a combination of surgical procedures. Finally, this study can be considered pioneering in that it is the first to evaluate the association of blood NfL with risk of post-operative cognitive dysfunction.

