Risks associated with the study include uncovering evidence of undetected cognitive impairment, which may be upsetting to the patient and family. At the same time, this information will be helpful in optimizing patient outcomes. Furthermore, patients will undergo a blood test for NfL that may result in brief discomfort.

Benefits of participating include the opportunity to obtain baseline cognitive testing results, which may better inform patients of current cognitive health. Furthermore, those patients who do end up performing abnormally on the MOCA will be referred for additional diagnostic work-up for dementia.

7. *Data Confidentiality and Privacy*

Data will be stored on a secured server with restricted access to the project folder. Participants will be identified by a study identification number. Secure surveys will be conducted through RedCAP. Data from the CRFs and the cognitive assessment score sheets will be entered into a secure RedCap database. A participant tracking database will also be created in RedCap. Neuroscience research study staff are experienced at building RedCap applications and using them for data entry and participant tracking.

8. *Timeline*

August 2019	Development of cognitive battery workflow
September 2019	Training of research staff in cognitive battery/submission to IRB
October 2019	Education of orthopedic providers re: cognitive assessment
November 2019	Initiate recruitment process
Nov 2019 – Feb 2021	Administration of cognitive battery at baseline and 3 months
March 2021	Data analysis

April 2021	Manuscript preparation/discuss at neurology & orthopedic meetings throughout organization
May 2021	Evaluate inclusion of cognitive battery as a standard clinical initiative in orthopedics
July 2021	Presentation at AAIC Conference
March 2022	AAOS Conference
June 2022	AOA Conference

9. Dissemination/Sharing Results/Integration and Impact

Results from this investigation will be shared during department meetings for neurology and orthopedic surgery, respectively. Furthermore, a presentation will be performed for the Regions HLT meeting as this was a Red-funded grant. Efforts will be made to discuss findings with Park Nicollet neurology and orthopedic departments if it is determined from this study that certain pre-surgical factors are predictive of post-operative cognitive dysfunction.

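### The exploratory risk-factor model selects and tests variables on the same data with no allowance for selection, so its p-values and odds ratios will mislead.

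*Combined protocol and SAP*

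**What the plan says.** Section 4.f of the combined protocol and SAP describes two risk-factor models under Secondary Aim 1. The first is prespecified: a logistic regression of POCD on five named factors, to which the plan adds "We will also include age and gender". The second is the one at issue: an exploratory model that brings in further risk factors and will "use score selection to keep variables with the most impact".

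For this second model the plan gives no candidate list, no number of candidates, no model size or stopping rule, no shrinkage and no internal validation. Section 3 mentions cancer, alcohol abuse and narcotic use, but only as examples. The opening paragraph of section 4.f states that all analyses are "evaluated at the 0.05 significance level, unless otherwise indicated", and nothing is indicated otherwise for the exploratory model.

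Section 4.g gives the size of the study ("The goal of the study is to recruit n=100 subjects") and the expected incidence ("We anticipate the POCD incidence rate will be between 18 and 25" percent). Its only calculation concerns the precision of the incidence estimate. Nothing there addresses Secondary Aim 1.

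**The concern.** Score selection ranks subsets of variables by their score chi-square. A variable is kept because it looks strong in these patients. Its p-value and odds ratio, computed afterwards in the same patients as if the variable had been named in advance, are therefore biased away from the null. Labelling the model exploratory tells the reader to be cautious, but it does not correct either figure.

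At stake is the credibility of the exploratory list. A factor with no relation to POCD could appear with p<0.05 and a large odds ratio. It could then be carried into the departmental discussions, the manuscript or the grant application that section 9 describes.

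**Working it through.** **1. The plan's own figure.** Section 4.g states: "A sample size of 100 produces a two-sided 95% confidence interval with a width equal to 0.157 when the sample proportion is 0.2". The simple asymptotic width is 2 × 1.96 × √(0.2 × 0.8 / 100) = 0.1568, which reproduces 0.157. The figure is right, but it says nothing about risk-factor selection.

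**2. Events.** 100 × 0.18 = 18 and 100 × 0.25 = 25, if every patient is evaluable. With 10% lost, the counts are 90 × 0.18 = 16.2 and 90 × 0.25 = 22.5. The prespecified model has 5 + 2 = 7 parameters, so 18/7 = 2.6 to 25/7 = 3.6 events per parameter. Ten further candidates would make 17 parameters, with 18/17 = 1.1 to 25/17 = 1.5 events each.

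**3. Benchmark.** If k independent null candidates were each tested at 0.05, the chance of at least one p<0.05 would be 1 − 0.95^k.

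**4. Simulation.**
- *From the plan:* n = 100, incidence 18% and 25%, level 0.05.
- *Assumed:* k = 3, 5, 10 or 15 independent candidates, all unrelated to POCD, about half binary (prevalence 10–40%) and half continuous; one, two or three variables kept; two-sided Wald tests.
- *Method:* the best subset of each size was chosen by score chi-square and the logistic model refitted. This was done with and without seven unrelated terms forced in to stand for the prespecified model. With those terms forced in, the ranking used a least-squares approximation to the score statistic. There were 2,000 replicates per setting.
- *Comparison:* n = 1,000 at 20% incidence (about 200 events), 500 to 1,000 replicates.

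Chance that at least one kept null variable has p<0.05:

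| Candidates k | 1 − 0.95^k | n = 100, 18–25 events | n = 1,000, about 200 events |
|---|---|---|---|
| 3 | 14% | 10–13% | not run |
| 5 | 23% | 18–23% | 21–22% |
| 10 | 40% | 33–45% | 37–42% |
| 15 | 54% | 43–62% | 52–57% |

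The ranges cover both incidences, all three model sizes, and the runs with and without forced terms. A separate simulation with 20 events and the best three kept gave 11%, 21%, 41% and 61%, in line with the table.

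**5. What the low event count does.** Moving from about 20 to about 200 events hardly changes the table, so k drives the rate. The odds ratios do change. When the single best variable was binary and reached p<0.05, its median apparent odds ratio (taken in either direction; the true value is 1) was 3.4–5.1 at n = 100, against 1.5–1.6 at n = 1,000.

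**6. Apparent discrimination.** With 20 events and the best three kept, the apparent c-statistic for pure noise was 0.61 to 0.71 across k = 3 to 15; the true value is 0.50. At k = 10, repeating the selection inside a bootstrap brought it from 0.69 to about 0.56. That removes much of the optimism, though not all.

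**The case against.** The strongest reply is that the plan already keeps this analysis in its place. The five factors of main interest are named in advance, with age and gender, and the selected model is separate and called exploratory. Neither the incidence estimate, the prespecified model nor the NfL models use the selected variables. This stands, and it limits the point to a minor one.

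Several stronger readings are tempting, and the documents do not support them:

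- *That the 18–25 events cause noise variables to look significant.* The rate is nearly the same with about 200 events. Few events exaggerate the odds ratios, which is a different fault.
- *That false findings will be frequent.* This is fair with about ten or more candidates, but the plan gives no count. With 3 to 5 the figure is 10–23%. The model size is assumed as well.
- *That score selection applies a 0.05 cut-off, or that the plan promises to declare kept variables significant.* It does neither explicitly. The test at 0.05 is inferred from the general sentence in section 4.f, which exempts no analysis. If no p-value were reported, the odds ratios would still be selected ones.
- *That section 9 commits the sponsor to act on the list.* It says that efforts will be made to discuss findings with other departments "if it is determined from this study that certain pre-surgical factors are predictive of post-operative cognitive dysfunction". The prespecified factors could trigger that discussion just as well.

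It is also fair to say that Secondary Aim 1 promises no c-statistic, so the inflated values in step 6 measure optimism and are not a fault in a planned output. Nor is penalised regression clearly the better tool. Ridge selects nothing. In 300 simulated null studies with 20 events, lasso at the minimum-deviance penalty by 10-fold cross-validation still kept at least one noise variable in 26%, 31% and 35% of studies for k = 3, 5 and 10. Only the one-standard-error penalty brought this down clearly, to 8–11%.

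**Conclusion.** The point holds in a limited form. As written, the exploratory model uses one set of data to choose variables and to test them, and neither its p-values nor its odds ratios allow for that. How much this matters turns on a number that the plan leaves open, the count of candidates: the false-positive chance is about twice the nominal 5% at the bottom of the range and about twelve times at the top (62/5 = 12.4).

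These figures assume independent candidates with no true effect, at most three kept, two-sided Wald tests, complete follow-up and the incidence anticipated in section 4.g. The plan's own rule for POCD, a decline of 1.5 SD in any test or domain, could yield a different event count. That would alter the inflation of the odds ratios more than the false-positive rate. This is an inexpensive improvement to make before analysis and no threat to the study's main conclusions.

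**What to change.** Amend the exploratory paragraph of section 4.f, Secondary Aim 1, as follows:

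1. List the candidate variables and fix the maximum number to be kept before any outcome data are analysed. State whether the seven prespecified terms are forced in.
2. Repeat the entire score selection in each bootstrap resample, and say how resamples in which the model fails to converge are handled.
3. Report how often each candidate is selected, with an optimism-corrected c-statistic. Note that at this sample size the correction may be incomplete.
4. Give no p-values after selection and make no significance claims for this model; exempt it explicitly from the general 0.05 statement. Describe kept variables as hypotheses for a larger cohort.

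Penalised regression is optional. If it is used, the penalty rule should be named in advance, because the results depend on it.

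The cost is SAP wording and modest programming on data already being collected, with no new visits or patients. The drawback is a less striking list: selection frequencies will probably show that few factors are chosen consistently.

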The term postoperative cognitive dysfunction (POCD) describes a deterioration of cognition that is temporally associated with surgery (Lezak MD Neuropsychological Assessment NY 2004). As opposed to delirium, POCD depends on valid assessments of preoperative and postoperative cognitive function. The underlying etiology of POCD remains unclear. Cerebrovascular disease, cerebral hypoperfusion, genetic susceptibility, alteration in neurotransmitter function, neurohumoral stress, and central nervous system (CNS) inflammatory phenomenon have all been suggested, but the principal suspect has been general anesthesia (Silverstein JH et al Anesthesiology March 2007). However, numerous studies suggest that choice of anesthesia is *not* an important factor in the development of POCD (Wu Reg Anesth Pain Med 2004).

There is an absence of guidelines related to orthopedic surgery and cognitive dysfunction risk to inform the decision-making process for proceeding with surgery in the elderly. The largest trial of POCD was published by anesthesiologists and looked at 1,218 patients aged ≥ 60 at baseline, 1 week, and 3 months post operatively, finding an overall incidence of 25.8% for cognitive dysfunction (Moller JT Lancet 1998). Increasing age, duration of anesthesia, little education, a second operation, postoperative infections, and respiratory complications were risk factors for early postoperative cognitive dysfunction (1 week post-op), but only age was a risk factor for late postoperative cognitive dysfunction (3 months post-op). Limitations to this study include the fact that results were not limited to a certain type of surgery (eg.

orthopedics) and a MMSE of ≥ 24 was used to define normal cognition in this population. Currently, the MMSE is seen as an insensitive screening test in which patients with mild dementia may still score within normal limits ≥ 24 (Lezak MD Neuropsychological Assessment NY 2004).

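### Secondary Aim 2 sets out to assess the predictive ability of NfL but plans no measure of prediction, and neither planned model shows what NfL adds before surgery

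*Combined protocol and SAP*

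**What the plan says.** Section 4.f states Secondary Aim 2 as to "explore the role of serum neurofilament light (NfL) in predicting risk for development of POCD". Two logistic models follow. The first has NfL as its predictor and is fitted "to assess the predictive ability of NfL in the development of POCD". For the second: "We will fit another logistic model that includes NfL and adjusts for the risk factors called out in Secondary Aim 1".

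No c-statistic, sensitivity or specificity, calibration, internal validation or comparison with known predictors is named. The only criterion is the general one, that analyses are "evaluated at the 0.05 significance level, unless otherwise indicated". Nothing says which of the two models supports the conclusion.

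Aim 1 numbers five risk factors: past delirium, delirium after the operation, type of anesthesia, more than three sedating drugs started in hospital, and earlier surgery under general anesthesia. Age and gender join the Aim 1 model in a separate sentence, outside that list. Section 3 reports from the largest earlier study that "only age was a risk factor for late postoperative cognitive dysfunction", meaning at 3 months.

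Section 4.g gives the size of the study: "The goal of the study is to recruit n=100 subjects". On incidence: "We anticipate the POCD incidence rate will be between 18 and 25" percent. Its one precision figure concerns the primary aim.

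**The concern.** The Summary (section 1) wants NfL to pick out, before the operation, patients who are more likely to develop POCD. That is a question of how well the marker separates future cases from non-cases, and of what it adds to facts already known before surgery. An odds ratio with a p-value answers neither. A marker can be clearly associated with an outcome and still separate patients poorly.

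The two planned models leave gaps of different kinds. The NfL-only model, the one tied to predictive ability, leaves out the only 3-month risk factor that the protocol cites. The second model mixes pre-operative facts with events that follow surgery, so its NfL estimate is not what a clinician could use beforehand.

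Section 9 plans to discuss findings with other departments if pre-surgical factors prove predictive, and hopes the publication will support a larger grant application. The plan gives no basis for judging whether NfL is predictive.

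**Working it through.** **Inputs from the documents.** n = 100; incidence 18% to 25%, so 18 to 25 events if all 100 are evaluable; significance level 0.05 (sidedness is not stated for Aim 2; two-sided assumed).

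**Assumptions.** NfL, on the scale analysed, is normal with equal variance in cases and non-cases (binormal); no loss to follow-up (no dropout rate is given).

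**1. The plan's own figure.** Section 4.g states a "two-sided 95% confidence interval with a width equal to 0.157 when the sample proportion is 0.2". Check: 2 × 1.96 × √(0.2 × 0.8 / 100) = 2 × 1.96 × 0.04 = 0.1568. It reproduces. No precision is given for Aim 2.

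**2. Weakest NfL effect that reaches p = 0.05.**
- SE of the log odds ratio per SD = 1/√(n p(1−p)). At 20 events: 1/√16 = 0.25.
- Just-significant log odds ratio d = 1.96 × SE. At 20 events: 0.49, and exp(0.49) = 1.63.
- c-statistic = Φ(d/√2). At 20 events: Φ(0.346) = 0.636.
- 95% CI for c from the Hanley-McNeil SE, about 0.073 at 20 events.
- At the mid-point cut, sensitivity = specificity = Φ(d/2); PPV follows by Bayes' rule. At 20 events: 0.597 × 0.2 / (0.597 × 0.2 + 0.403 × 0.8) = 0.27.

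| Events | OR per SD | c-statistic | 95% CI | Sens = spec | PPV | Base rate |
|---|---|---|---|---|---|---|
| 18 | 1.67 | 0.641 | 0.49 to 0.79 | 60% | 25% | 18% |
| 20 | 1.63 | 0.636 | 0.49 to 0.78 | 60% | 27% | 20% |
| 25 | 1.57 | 0.626 | 0.49 to 0.76 | 59% | 32% | 25% |

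The lower limits fall just under 0.5 although p = 0.05 because the two standard errors are different approximations.

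In 3,000 simulated trials with 20 events, a marker with a true c-statistic of 0.60 was significant in 27% (30% by formula). Its mean observed c-statistic in those trials was 0.68.

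**3. What the second model can show.** It holds NfL plus five factors (6 parameters), or 8 with age and gender.
- Events per parameter: 18/6 = 3.0 to 25/6 = 4.2, or 18/8 = 2.3 to 25/8 = 3.1.
- On either reading it contains post-operative delirium and sedating drugs added in hospital, which are unknown before surgery.

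**4. Age as a stand-in, conditional only.** The documents give no NfL-age correlation and no odds ratio for age. Both are assumed here: age odds ratio 1.5 to 2.5 per SD, correlation 0.3 to 0.7. The simulation used 3,000 trials per scenario, n = 100, 20% POCD, and an NfL with no effect once age is known.
- NfL-only model: significant in 7% to 61% of trials (23% at odds ratio 2.0, correlation 0.5).
- With age in the model: 4% to 5%.

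**5. Precision after the change.** The 95% half-width for a true c-statistic of 0.60 is 0.150, 0.144 and 0.132 at 18, 20 and 25 events. For 0.70 it is 0.145, 0.138 and 0.126.

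**The case against.** The aim is labelled exploratory, the study is observational, and NfL guides no treatment. The strengths section (4.h) speaks only of association, and the grant is a hope expressed for the publication as a whole. This stands, and it limits the weight of the point.

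Four stronger readings are tempting, and the documents do not support them.
- *NfL will be called predictive if p < 0.05.* No such rule is written. That the coefficient test decides Aim 2 is inferred from the general 0.05 level; the plan is silent on outputs and criterion.
- *NfL is never adjusted for age.* If the Aim 1 risk factors are read to include age and gender, the second model does adjust for age and largely meets that worry. If they mean only the five numbered factors, it does not. The text allows both.
- *The second model's covariates are unknown before surgery.* Past delirium and earlier general anesthesia are known. Only post-operative delirium and in-hospital sedating drugs are clearly later.
- *NfL is a proxy for age.* No correlation is documented. With assumed correlations of 0.4 to 0.6 and age odds ratios of 1.5 to 2, a pure proxy would show about exp(0.4 × ln 1.5) = 1.18 to exp(0.6 × ln 2) = 1.52. That is below the just-significant 1.57 to 1.67, so the expected proxy effect alone would not reach significance, although some trials would.

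It can also be said that with 18 to 25 events a difference in c-statistic will be imprecise. That is true. It is a reason not to make that difference the only test of prediction, but a wide interval still tells the reader how little is known, which a p-value hides.

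**Conclusion.** The point holds in limited form. Aim 2 asks about prediction and plans only models of association. At this sample size a just-significant NfL effect corresponds to a c-statistic of about 0.63 to 0.64, with an interval reaching down to about 0.49, and a mid-point cut would raise the probability of POCD by only about 7 percentage points over the base rate. These figures rest on the binormal assumption and full follow-up; losses would widen the intervals.

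Neither planned model shows pre-operative value: the first omits age, and the second conditions on post-operative events whichever way its covariates are read. How far NfL might merely reflect age cannot be settled from the documents. This is a cheap improvement to an exploratory secondary aim. It does not affect the primary aim.

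**What to change.** In section 4.f, Secondary Aim 2:
- Report the c-statistic with a 95% CI, bootstrap optimism-corrected, for NfL alone and for a pre-operative model of age and gender with and without NfL. Give the likelihood-ratio test for adding NfL.
- State that age and gender are in the adjusted model.
- Describe the unadjusted odds ratio as association, and base any statement about prediction on the discrimination and added-value results together.

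Age, gender and NfL make three parameters, so 18/3 = 6 to 25/3 = 8.3 events per parameter, which is easier to support than the planned second model.

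The cost is a few lines of SAP text and a short bootstrap on data already being collected. The downside is a less favourable-looking result, with a c-statistic known only to about ±0.13 to ±0.15.

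### With at most 18–25 expected events, the multivariable POCD models name no sparse-data method, and neither planned NfL model estimates what NfL adds to factors known before surgery

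*Combined protocol and SAP*

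**What the plan says.** Section 4.g sets n=100 from feasibility and budget and gives the expected event rate: "We anticipate the POCD incidence rate will be between 18 and 25" per cent. Its only precision figure concerns the incidence estimate.

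For Secondary Aim 1, section 4.f states: "We will fit a logistic regression model with presence of POCD as the outcome of interest and the above risk factors" as predictors. Five factors are listed: history of delirium, "Presence of post-operative delirium", "Regional versus general anesthesia", ">3 sedating medications added during hospitalization", and prior surgery under general anaesthesia. A separate sentence follows: "We will also include age and gender". Score selection is mentioned only for an exploratory model with further variables.

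For Secondary Aim 2 there are two models. The first has "NfL as the predictor of interest to assess the predictive ability of NfL in the development of POCD". The second is described in one sentence: "We will fit another logistic model that includes NfL and adjusts for the risk factors called out in Secondary Aim 1".

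No penalised, exact or other sparse-data method is named. NfL is drawn at the screening/baseline visit (section 4.d), and the Summary gives its purpose as finding patients at higher risk before the operation. Section 4.h concedes that there is no cognitive assessment soon after surgery of the kind that might reveal delirium.

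**The concern.** There are two separate issues.

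**Sparse data.** With few events per term, maximum likelihood pushes odds ratios away from 1 on average. If every recorded case of a binary factor has the same POCD outcome, that factor's odds ratio has no finite estimate. Two of the five listed factors are delirium variables, and the limitation in section 4.h suggests that recorded post-operative cases may be few. Secondary Aim 1 is the more exposed, because those odds ratios are its result.

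**Conditioning set.** Post-operative delirium and sedatives added in hospital are unknown when NfL is drawn. They suit Secondary Aim 1, which asks about peri-operative factors. Used to adjust NfL, they leave the pre-operative question unanswered: does NfL add anything to age and history? The NfL-only model gives crude prediction and cannot answer it either. It is also unclear whether age and gender, named outside the numbered list, enter the adjusted NfL model.

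**Working it through.** **The plan's own figure.** Wald width = 2 × 1.96 × √(0.20 × 0.80 / 100) = 0.1568, which reproduces the stated 0.157. It says nothing about the regression models.

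**Events per term** (events = n × incidence; each term 1 df). At n=100: 100 × 0.18 = 18 and 100 × 0.25 = 25. No dropout rate is given; the n=90 column assumes 10% loss (16.2 to 22.5 events).

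| Model | Terms | n=100 | n=90 |
|---|---|---|---|
| Secondary Aim 1: 5 factors + age + gender | 7 | 18/7 = 2.6 to 25/7 = 3.6 | 2.3 to 3.2 |
| Adjusted NfL, listed factors only | 6 | 18/6 = 3.0 to 25/6 = 4.2 | 2.7 to 3.75 |
| Adjusted NfL with age and gender | 8 | 18/8 = 2.25 to 25/8 = 3.1 | 2.0 to 2.8 |
| NfL only | 1 | 18 to 25 | 16.2 to 22.5 |

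**Bias in the NfL estimate (simulation; the inputs are assumptions, since the documents give none).** n=100, 8 terms, 1,000 to 2,000 runs per scenario.
- Prevalences: each delirium factor 5, 10 or 20%; prior general anaesthesia 85%; general anaesthesia 50%; sedatives 30%.
- Odds ratios: NfL and age 1.5 per SD (correlation 0.5), post-operative delirium 3, history of delirium 2, anaesthesia type and sedatives 1.5, the rest 1.
- Maximum likelihood: mean NfL log odds ratio roughly 1.1 to 1.2 times the truth (1.08 to 1.23 across all runs). A true odds ratio of 1.50 then reads about 1.50^1.1 = 1.56 to 1.50^1.2 = 1.63. Interval coverage was 93–96% and type I error 5–7%.
- Firth: 0.95 to 1.03 times the truth, with root mean squared error 14–19% lower.

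With different assumed inputs (odds ratio 2 for each listed factor, 3,000 runs), maximum-likelihood fits that converged gave a mean log odds ratio of 0.47–0.48 against a true 0.405, about 16–19% too large.

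**Chance of a zero cell for a delirium factor.** With d recorded cases and POCD risk q among them, P = q^d + (1−q)^d. The range q = 0.18 to 0.40 is an assumption.

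| d | q = 0.18 | q = 0.40 |
|---|---|---|
| 3 | 56% | 28% |
| 5 | 0.82^5 + 0.18^5 = 37% | 0.60^5 + 0.40^5 = 9% |
| 10 | 14% | 0.6% |

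In the simulations, at least one of the two delirium factors had a zero cell in 31–39% of studies at 5% prevalence, 4–10% at 10%, and about 1% or less at 20%.

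**Size of the conditioning effect.** Large-sample fits (n=400,000; delirium 5–20%, delirium odds ratio 3) set the NfL odds ratio at 1.50 in the 8-term model. The corresponding pre-operative NfL odds ratio was:
- 1.47–1.49 if NfL does not affect delirium (non-collapsibility only);
- 1.51–1.54 if NfL raises delirium with odds ratio 1.25 per SD;
- 1.55–1.69 if that odds ratio is 2 per SD.

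**The case against.** The strongest case on the other side is that little of this would change a conclusion. The bias in the NfL log odds ratio is about 0.14–0.20 of its sampling SD, or 2–4% of mean squared error, and the 95% interval for the odds ratio spans roughly 3.4- to 3.9-fold. The NfL-only model has 18–25 events for one term and conditions on nothing post-operative. The second model asks a legitimate question about association given peri-operative factors. Secondary Aim 2 is worded as exploratory. Firth cannot repair poor recording of delirium. A five-term pre-operative model still has only 18/5 = 3.6 to 25/5 = 5.0 events per term.

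All of that stands, and it limits the point. It does not remove it. The incremental pre-operative question remains unanswered by either NfL model, and Firth had smaller bias and error at almost no cost.

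Three stronger readings are tempting:
- *Maximum likelihood will produce false NfL findings.* Coverage and type I error stay close to nominal in the simulations.
- *The delirium odds ratios will be inestimable.* That depends on a prevalence the documents do not give, and section 4.h does not say how delirium will be recorded.
- *NfL will look predictive merely because age is left out.* This needs the 6-term reading. The 8-term reading is the natural one: age is in the Secondary Aim 1 model, and the Background lists it among the variables to be evaluated. The wording needs settling, but it does not show that age is omitted.

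**Conclusion.** The point holds as a recommended improvement to the secondary analyses. The event and term counts follow from the plan itself, with 18–25 events as the ceiling before any loss to follow-up. The roughly 10–20% overstatement of the NfL log odds ratio rests on assumed prevalences and effects, and on the inference that ordinary maximum likelihood is meant. The zero-cell risk (9–37% with 5 recorded cases, 0.6–14% with 10) rests on an assumed POCD risk of 18–40% among those cases.

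The conditioning issue concerns which question is answered more than the size of an error. A reader might infer that adjusting for post-operative factors seriously distorts the NfL result. The documents give no evidence that NfL affects delirium, and the gap is near nil unless that effect is strong. The primary incidence estimate is unaffected.

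**What to change.** 1. Fit the multivariable POCD models by Firth-penalised logistic regression with profile-penalised-likelihood confidence intervals (SAS PROC LOGISTIC, MODEL options FIRTH and CLODDS=PL).
2. Keep the NfL-only model and add a pre-operative adjusted model, also by Firth: NfL, age, gender, history of delirium, and prior surgery with general anaesthesia. Include anaesthesia type only if it is fixed before surgery, which the documents do not say. Firth is needed here too: under the assumed inputs, maximum likelihood separated in 19–30% of studies at 5% delirium prevalence, 6–11% at 10% and 4–8% at 20%.
3. Keep the planned NfL model with peri-operative factors as secondary, and state in one sentence that age and gender are in it.

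The cost is SAP wording, one more model and an option in software already named; no new data are needed. The downsides should be stated:
- Odds ratios are shrunk slightly.
- Intervals stay wide at n=100. The upper-to-lower ratio for the NfL odds ratio is about 3.2 to 3.7 in the five-term model and 3.4 to 3.9 in the eight-term model.
- Plain Firth raises mean predicted risk (about 20% against 18%, 26.5% against 25%), so the intercept should be re-estimated if predicted risks are reported.
- Any under-recording of delirium is not corrected.
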